## **Innovation**

The proposed robotic hand orthosis has significant potential to restore hand functionality in a population underrepresented in prior robotic glove and exoskeleton studies due to the localized yet complete nature of their nerve damage and the wide variability in resulting impairment. Our research aims to remedy the shortcomings in previous strategies to create a lightweight and portable robotic hand orthosis. It is our belief that the proposed orthosis is innovative due to its combination of portability and dexterity, enabled by novel actuation and control methodologies developed by our team. While the approach is exploratory, the orthosis has the potential to return grasp functionality and dexterity to patients suffering from an injury that often results in significant levels of disability. Integration of an intuitively controllable, lightweight and portable robotic hand orthosis would lead to significant improvements in quality of life and ability to re-enter the workforce following a serious traumatic injury. In addition to the minimal form factor of the orthosis, the finger mechanisms ensure natural bending utilizing side-mounted linkages, a novel rigid orthosis solution based on an extensive literature review.

Furthermore, the orthosis will be operated through a small set of verbal commands that correlate with an equally small set of archetypal grasp groups defined by their interaction with similar object geometries. These groups encompass the 33 common grasps defined in [26]. Upon receiving the command for one of these groups, i.e. "Cylinder", the system will begin to flex the fingers through a progression of the grasps in that group, each targeted at grasping sequentially smaller objects. The temporal patterns and naturalistic motion paths are characterized by grasp mappings via Principal Component Analysis (PCA) [7]. Once the regression model determines the orthosis has reached a defined degree of similarity with a grasp, the motion will stop. When the grasp is to be released, the user simply says "Open" and the orthosis will release the commanded grasp.

Finally, the addition of wrist flexion/extension actuation in tandem with grasping motions will enable natural and comfortable action. The robotic hand orthosis is designed to restore the majority of pinch and grasping functionality to both fully and partially paralyzed hands. While outside the purview of the proposed study, the orthosis may also be used as a combination rehabilitation-biofeedback device during recovery from surgical treatment while waiting for nerves to regenerate. The orthosis would keep joints supple, avoiding contractures, and provide biofeedback of the extremities, which could potentially enhance recovery post-surgery. This functionality will be explored in future studies.

## **Approach**

### **Aim 1: Design and prototype a robotic hand orthosis that provides grasp assistance for patients suffering from hand paralysis due to brachial plexus injuries**

**Overall Strategy:** The objective is to produce a lightweight, portable, intuitively controllable, and compact rigid orthosis to increase the manual dexterity of adult patients whose hands are paralyzed due to nerve damage. This will help improve the quality of life for patients with brachial plexus injury, as surgical options are limited for adult patients. Our team's previous expertise in designing, prototyping and integrating of robotic exoskeleton gloves in addition to the medical expertise from the clinical team members will be leveraged to create an orthosis to provide maximal assistance to the patients.

**Preliminary Studies:** Current robotic exoskeletons, gloves, and orthosis technologies are thoroughly

described in review literature [2], [27], [28]. Upon a meta-review, it can be seen that such devices are often too large for everyday use, require significant exterior actuation units, and utilize user control systems that either amplify existing hand motions or incorporate EMG inputs. Generally, when building robotic exoskeletons and orthoses, researchers follow one of two design methodologies. In the first case, a rigid exoskeleton is used to apply forces at the locations where the tendons of the hand normally apply forces, resulting in a large and protuberant rigid outer frame, or, as in the case of the Rutgers glove, a rigid structure mounted on the palm of the hand [29], [30]. The CyberGrasp® [31] and the Festo ExoHand [32] are both state-of-the-art commercial exo-gloves that, while providing impressive levels of dexterity, have large and bulky profiles that preclude their use day-to-day.

[figure not shown]
An alternative approach is the application of soft robotics principles for gloves and orthoses. However, many of these innovative designs are still rather thick due to the need for inflatable segments to induce bending and require compressors and air storage cylinders to operate [33], [34], which hinders the user's mobility. The pneumatic inflatable actuators also have difficulty approximating natural flexion. Alternatively, exoskeleton gloves that utilize routed cables for actuation are another approach for robotic gloves [35], [36]. However, tendon-driven gloves may require uncomfortable pre-tensioning, experience significant efficiency losses due to cable friction, and require bulky actuation units often worn on the waist/backpack. In addition, the cables are generally fixed at points on the glove by sewing them into the fabric, which introduces undesired and uncomfortable shear forces on the finger and may cause slippage/twisting of the fabric, which disrupts proper force application and reduces repeatability.

User control is another important aspect of robotic orthoses. Devices such as the Exo-glove [36] detect wrist motion and treat that as a signal to initiate finger actuation, while the NASA/GM RoboGlove [37] uses the small force changes induced when the user's fingers contact the glove surface as a signal to apply force in a certain direction. For those with brachial plexus injury, the hand may be fully paralyzed and the wrist motion can be impaired or non-functional as well. This limitation precludes such control approaches. Other prostheses and glove systems utilize EMG inputs; however, fine muscle control of the injured arm can be challenging or impossible with this type of injury [38], [39].

The proposed orthosis is intended to provide natural bending and repeatability as a rigid exoskeleton, while retaining a minimal form factor. Research on the typical grasping actions of the human hand were utilized to guide the design of the linkage mechanism [40]–[42]. In addition, the orthosis emphasizes design compactness and motion efficiency [43].

**Research Design:** The key aspect of this aim is to optimize the design of the robotic hand orthosis and integrate a robust working prototype. The design concept is shown in Figure 2. For rapid prototyping purposes, the current design is shown using 3D printed polymer. The orthosis is designed to minimize the number of actuators while optimizing the ability to approximate tip, three jaw chuck, and lateral pinches [44] as well as cylindrical, spherical, and hook grips [45].

The compact size and high level of control possible with this system are enabled by our novel actuator design. Two proof-of-concept actuators developed in the PI's lab are shown in Figure 3(a) which utilize a series elastic actuator (SEA) for indirect force measurement [46]. The use of SEA allows for indirect measurement of force applied directly from the actuators without utilizing contact sensors at the fingertips. Our new actuator design, seen in Figures 3(b) and 3(c), is comprised of the same key components as the proof-of-concept, yet will be at least 30% smaller than the original by incorporating a magnetic encoder and compact drive components. Furthermore, the actuator is an order of magnitude faster, allowing the user to fully traverse the joint space in approximately 0.4 seconds. The actuator is non-backdrivable due to high gear ratio of the gearbox. Therefore, when the

**Figure 2.** Proposed Robotic Hand Orthosis Design

[figure not shown]
fingers go to a set position, they will remain in that position even after forces in the opposite direction are applied. This helps to reduce power consumption due to motor operation. Furthermore, the springs in the actuator provide compliant distribution of the grasping forces applied, thereby assisting in gripping non-uniform objects and maintaining the desired grip force.

The links of each articulated mechanism driving individual fingers using the SEA are kinematically coupled in that there is one motor for three degrees of freedom (DOF) per finger corresponding to flexion/extension. Each actuator will drive the corresponding finger's flexion through the mechanism. The articulated mechanism itself is composed of two four bar linkages connected in series and is detailed in previous works done by the lab [6], [8]. The finger linkages have extremely thin profiles (~2 mm), which allow for a comfortable fit between the fingers. While finger adduction/abduction is not actively controlled with this prototype, fingers are held slightly apart at fixed angles by the linkages. These angles are adjustable and can be set to the most comfortable position for each user. Thumb abduction/adduction will be driven by a rotary motor fixed to the main hand plate, and thumb flexion will be driven by an actuator of the same style as those for the fingers, mounted on the back of the thumb's base on a small plate driven by the rotary motor. When a human grasps, the wrist extends in a coupled motion, with studies finding the minimum optimum angle of wrist extension to be 25° [47]. The orthosis is designed to possess this wrist extension/flexion capability, utilizing a similar link mechanism as that of the fingers to provide symmetric 30° extension/flexion. The actuators each have sufficient force output to prescribe a fingertip force exceeding 40 N, the average 180° distal pad press force per finger found in one study [48], and allowing for a thumb-index pad pinch exceeding 60 N, the largest average pinch force reported across several studies [42], [47], [48].

Throughout the design process, the design engineers will meet with [name], therapists, and patients with brachial plexus injury to ensure stakeholder input is leveraged in the design. Drawing upon the PI's experience from previous working prototypes built in the lab, the driving components and the battery packs for the orthosis are chosen such that the system can function for a day without recharging. The orthosis has six motors, each with a nominal draw of 0.1 A and stall current draw of 0.35 A. The ARM Cortex-M4 microcontroller, along with the associated electronics, has a max draw of 150 mA during operation. With a battery of 7.4 V and 2500 mAh the device can run continuously for two hours under full load. The battery is small, at 10x5x2.5cm in dimension and almost 100 g. The SEA and the non-back drivable nature of the transmission system allows the orthosis to maintain its grip force without actively drawing current, therefore, along with the intermittent frequency at which objects are grasped, the device can be expected to last one full day without recharging.

The proposed orthosis is intended to weigh around 250 g without the battery source. The resulting total mass thus approaches 350 g, enabling long term use with minimal fatigue. Additional ergonomic factors were also considered in the design. One such is the novel finger linkage design, allowing for misalignments between the axes of rotation of the mechanism and those of the finger joints [6], [11]. Additionally, the linkages are fixed to the fingers with semi-rigid finger rings that leave the finger pads exposed, to accommodate patients who do possess some sensation in their fingers. Furthermore, in order to adjust finger lengths variation between patients, the final link length is adjustable. For comfort while wearing the system, the wrist actuator is also stitched into a stretchable fabric sleeve worn on the forearm, along with the microcontroller unit, motor drivers, communication modules and batteries, while the forearm sleeve is fixed securely to the arm with Velcro closures.

The control of the orthosis will revolve around the ability to predict the finger configuration necessitated by the grasped object through the use of a predictive controller. The common grasps can be described accurately using a

**Figure 3.** (a) Proof of concept actuators; (b) proposed actuator prototype; (c) detailed actuator configuration

set of six vectors in latent space [49] that encompass the motions of the 21 DOF of the human hand [50]. The latent space for the system is the domain containing the geometrical mapping of the complex hand motions into a smaller collection of six coordinated motions. The 33 common grasps from [26] can be grouped via PCA according to their spatiotemporal relationships [51] or to their interaction and configuration geometries [7].

As the springs in the SEA deform when the fingers interact with the object, the necessary final grasp configuration for that object can be predicted by mapping each joint velocity to the latent space. The required grasping force per finger, as determined by the grasp paradigm and validated through benchmarking by the researchers, can then be exerted. The prediction will be performed using a novel matching algorithm. The definition of these latent variables varies from subject to subject but follow very similar trends, as shown in [52], allowing a general model to be applied. However, the efficacy of a calibration stage performed with the user's healthy hand, if possible, will be explored in lab testing.

The operation of the glove will be initiated via a voice command correlating with one of six grasp groups that will be processed via the onboard ARM Cortex-M4 microcontroller using readily available open source libraries from ARM [53]. The libraries provide lightweight voice recognition neural networks, allowing the system to recognize a user's tonal frequency when providing commands following a short training session. The verbal grasp commands are: Cylinder, Sphere, Tripod, Tip, Lateral, and Extension. More user-friendly names may be chosen with assistance from ION therapists. To give an example, in this categorization, the group "Cylinder" contains the grasps for large, medium, and small cylinders, characterized by increasing amounts of equal flexion along all the fingers. After receiving this command, the orthosis would thus flex all fingers simultaneously until contact is detected through joint velocity changes, at which time it would be able to command the degree of flexion required for the level of cylindrical grasp needed to grasp the detected object. Once the algorithm ascertains the orthosis has reached a set degree of similarity with a grasp, the motion will stop. To release, the user simply says "Open" and the orthosis will return to a neutral position.

**Goal:** The robotic hand orthosis will be considered a viable design if it can provide a controlled 40 N of force to each finger linkage, complete the finger flexion within 0.4 seconds, and can perform fundamental grasping and pinching motions in lab testing .

**Expected Outcomes:** This aim is intended to produce a mature and robust prototype that can be used in the feasibility test outlined in Aim 2.

**Potential Problems and Alternative Strategies:** The orthosis linkages are designed to be fixed to the fingers with Velcro-tightened finger sleeves. However, should an issue with finger slippage arise, the mechanism can be sewn onto a neoprene glove at key points to provide more fixation points. The overall glove mechanism is exposed for easy access for testing and adjusting, however a second, larger glove can be worn over the entire device to reduce the mechanical appearance if so desired.

## **Aim 2: Perform a pilot study on a small group of patients with hand paralysis due to brachial plexus injury**

**Overall Strategy:** The objective of this aim is to perform a feasibility study of the robotic hand orthosis through direct testing on affected patients. Six participants suffering from partial to full unilateral (one-sided) hand paralysis due to brachial plexus injury will wear the orthotic device to perform a list of everyday tasks. The patients will then report if the use of the robotic orthosis has resulted in an improvement in the dexterity and mobility of the hand.

**Preliminary Studies:** While surgical interventions exist for brachial plexus injuries, the methods used in returning motion and control to the upper and lower arm have not had the same level of success when applied to the hand. Patients who have suffered such an injury generally average scores in the 50s when evaluated with the DASH prior to surgery, and in the 40s following surgery [23], [54]. The preoperative scores indicate a severe disability, and the postoperative scores show large variation due to the hit-or-miss nature of the surgeries. The difficulty of restoring hand functionality via surgery is the cause of much of the remaining disability. A robotic orthosis has the potential to provide a significant increase in hand functionality for such patients.

**Research Design:** The Southampton Hand Assessment Protocol (SHAP) provides an excellent standardized test that include a series of 26 actions that include both abstract motions as well as selected ADLs for evaluation of hand functionality [18]. The actions can be grouped according to six major prehensile grasps to which the actions correspond. Patients are evaluated based on the time

### Timetable

This is a 24-month project with the following tasks and timeline: Complete design and perform physics-based simulations (mos. 1-8), fabricate, integrate, test and refine capabilities of a robust prototype (mos. 8-16), perform feasibility tests with patients and use the results to improve design (mos. 16-24). [name] will lead the design process of the robotic hand exoskeleton orthosis. Monthly in-person meetings during the design phase of the project at ION in Roanoke, Virginia will allow the design team to receive expert advice and input from [name], as well as from occupational/physical therapists familiar with brachial plexus injuries. Weekly in-person meetings between the two teams will commence once the project has progressed to the feasibility study, led by [name]. Both teams will work together to conduct the trials. Throughout the duration of the project, weekly teleconferences will be held when there is no in-person meetings scheduled in order to keep all members of the project up to date.

### Future Directions

The robotic hand orthosis presented is envisioned to potentially return a measure of functionality to those suffering from full or partial paralysis of the hand, resulting in a significant increase in quality of life. Upon the successful completion of the feasibility study and the incorporation of insights gained from it, a larger clinical trial to test and demonstrate the functionality of the glove on a wider patient pool could be conducted. Ultimately, the orthosis could be one day prescribed to patients following a unilateral paralysis-inducing injury. In addition, the compliant nature of the orthosis lends itself to uses in rehabilitation as well as grip assistance for patients with other types of hand disabilities. The system could be utilized by physical therapists to perform guided therapy. In patients with some finger function, the SEAs can be modified to detect motion and amplify it in a controlled fashion.

## **Recruitment and Retention Plan**

The participants in this study will be recruited on a volunteer basis by [name] and his office through in-office contact. As the study is a one-time event, retention strategies are not required.

## **Study Timeline**

One year after notice of award, [name] and his office will begin inquiring among patients with a brachial plexus injury on interest in volunteering for an hour in order to test the orthosis. As participants are recruited, team members from [name] lab will travel to the Carilion Institute for Orthopaedics and Neuroscience to conduct the tests at the participants' availability. Approximately 18-20 months following the notice of award, the study will be concluded.

## Protection of Human Subjects

Recruitment of human subjects will start following reception of IRB approval and the completion of the prototype. All investigators have received appropriate training in experiments using human subjects.

### Risks to Human Subjects

Human Subjects Involvements and Characteristics: Subjects will be adults, male or female, over 18 years of age. There will be no restrictions related to race or ethnic group. Subjects will have suffered a brachial plexus injury that left the hand of the injured armed with some degree of paralysis or impaired motion. The subjects will be asked to perform a list of actions with and without a robotic hand orthosis and compare their ability to perform their actions in a survey. All experiments with human subjects will take place at the Carilion Clinic Institute for Orthopaedics and Neurosciences (ION). The doctors, occupations/physical therapists, and researchers at ION are familiar with performing evaluations of hand function as well as hand research.

*Inclusion criteria:*

1. Patients with Brachial Plexus injury
2. Pan plexus or lower root injuries (C7, C8,T1)
3. 18 y/o - 69 y/o
4. No significant hand/wrist contractures or associated deformities
5. No open wounds in affected hand/wrist
6. Able to provide consent for treatment and follow general directions

Sources of Materials: Research material to be obtained from subjects will include length of time since injury, qualitative survey data on the fit and operation of the orthosis, participant performance on the Southampton Hand Assessment Procedure (SHAP), a clinically approved and standardized hand function test, both with and without the use of the proposed orthosis. Images of the hand as well as videos showing operation of the device with no identifying information may be recorded. This material will be secured in password protected, encrypted files only accessible by the study investigators. Any material used in publications will not contain identifying information.

Potential Risks: The actions performed in this study are limited to actions performed by the hands in day-to-day life, and they represent minimal risk of injury to the subject. Additionally, malfunction of the robotic orthosis is an additional source of risk in this study. However, this event is unlikely. The specific concerns relating to this as well as the actions taken to mitigate them are presented in the following section.

### Adequacy of Protection Against Risks

Recruitment and Informed Consent: The subjects will be recruited from the ION outpatient clinic pool. The potential subjects will meet with the study investigators and will be offered the IRB-approved informed assent form. If participants need additional time to think about their participation, they will be sent home with the assent form for their review. The researchers will be available at any time to answer questions regarding the study. Participation is voluntary and may be discontinued at any time.

Protection Against Risk: Subjects will be seated or standing during the hand function trial, whichever the subject deems more comfortable. The adjustable portions of the orthosis will be adjusted for each subject to ensure comfort and ease of use. To protect against physical risk, subjects will be closely monitored during the trial and data collection in the event of any malfunction or discomfort while using the hand orthosis. The study will be conducted in the presence of both engineers who designed the orthosis as well as physical therapists and other medical professionals in order to ensure the safety of the participants.

To protect against identity risk, study data will be identified only by a subject code and the document that links the code to the subject name will be password protected and stored separately from the data files pertaining to the study.

The risk of Robotic Hand Orthosis malfunction is very small but must be considered. Therefore, the following is a list of possible orthosis issues and the steps taken to prevent their occurrence.

**Pinch Points:** The orthosis will be designed specifically with the ergonomics in mind, and will be fitted over a form-fitting, thin glove in order to reduce chances of pinching. Additionally, mechanical stops will provide protection against pinches.

**Hyperextension/hyperflexion of fingers and wrist:** As stated previously, the orthosis will be designed with mechanical stops to prevent the fingers and wrist from moving in excess of their natural range of motion. In addition, electronic/software limit stops will detect if each planned range of motion passes its desired range and will immediately shut down the system.

**Power Failure:** In the event of power loss, the orthosis may be removed while in any grasp formation through unclasping the fingertip fixtures then sliding the hand out of the device.

**Controller Malfunction:** Should the controller malfunction, the mechanical limitations of the device will protect the hand from any injurious motion while the user or researcher switches off the device.

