## Specific Aims

The brachial plexus is a network of nerves that transfers signals which provide motor function and sensation to the shoulder, arm, hand, and fingers. The network originates in the cervical spinal cord (neck) and extends to the shoulder, arm, hand and fingers. While injuries to this region may occur in newborns during birth, they can be successfully repaired via surgical intervention; however, when caused by trauma in adults, injury to the brachial plexus can result in paralysis of the shoulder, arm, and hand with varying degrees of severity. In such cases, surgical options have had success restoring shoulder and arm function, but less so in returning sensation and mobility to the hand [1].

Robotic exoskeletons, gloves, and orthosis have been active research subjects for many years [2]; however, structural and operational hurdles make them impractical for wide spread use by patients. Current systems, whether rigid exoskeletons or pneumatic/cable actuated soft systems, often require large external actuation systems, and may not properly track natural finger flexion if not perfectly aligned. Both features result in a device that is neither portable nor comfortable. Moreover, prior designs are often controlled via electromyography (EMG) sensors attached to the injured arm, or by sensing finger motions of the injured hand and magnifying them. However, due to the full arm and hand paralysis faced by patients suffering from brachial plexus injury, this is not always a feasible control method.

Our long-term objective is to develop an intuitively controlled robotic orthotic solution designed to restore a measure of grasping ability and hand functionality in daily activities to greatly improve quality of life for patients with various levels of hand paralysis and loss of sensation due to brachial plexus injury. Our previous work on exoskeletons and robotic gloves [3]–[17] as well as our partnership with the expert surgeons and occupational hand therapists at the Carilion Clinic Institute for Orthopaedics and Neurosciences, puts us in an excellent position to provide such a solution. The goal of the present application is to design and integrate a prototype robotic hand orthosis and perform a pilot test involving a small number of patients with brachial plexus injuries to study the design's feasibility.

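### Safety monitoring looks for malfunction or discomfort, but eligible hands may lack sensation, and no hand check after use or adverse-event record is planned

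*Combined protocol and SAP*

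**What the plan says.** **What is watched for.** Adequacy of Protection Against Risks states that "subjects will be closely monitored during the trial and data collection in the event of any malfunction or discomfort while using the hand orthosis". The same section says that the engineers, physical therapists and other medical professionals will be present. The Data and Safety Monitoring Plan adds trained medical monitoring for the whole of the study session.

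**Who may be enrolled.** Specific Aims describes the target population as "patients with various levels of hand paralysis and loss of sensation due to brachial plexus injury". Aim 2 plans for "Six participants suffering from partial to full unilateral (one-sided) hand paralysis due to brachial plexus injury". Both lists of inclusion criteria (Aim 2, Research Design; Risks to Human Subjects) admit pan plexus and lower root injuries, and neither mentions sensation. The Aim 1 Research Design describes "semi-rigid finger rings that leave the finger pads exposed", a feature meant "to accommodate patients who do possess some sensation in their fingers". That wording treats sensation as something only some wearers have.

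**What covers the hand.** Under Pinch Points, the orthosis "will be fitted over a form-fitting, thin glove in order to reduce chances of pinching".

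**What is recorded.** Risks to Human Subjects and the Data and Safety Monitoring Plan list the same data: time since injury, a survey on fit and operation, SHAP performance, and optional images and videos. Neither lists adverse events or findings on the hand.

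**How long.** The Recruitment and Retention Plan says: "As the study is a one-time event, retention strategies are not required". The Study Timeline puts the session at about an hour.

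**The concern.** Of the two things staff are told to look for, an observer can see malfunction. Discomfort usually has to be reported by the participant, and a participant whose hand has no feeling cannot report it dependably. Fitting and the survey have the same weakness: finger angles and adjustments are set by comfort, and the survey on fit is self-report.

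A device working as designed can still load the skin and joints, and that is neither a malfunction nor, for an insensate hand, a felt discomfort. If nobody is asked to look at the hand afterwards and there is nowhere to write down what is seen, such an effect may leave no trace in the study data. Future Directions envisages a larger trial after a successful feasibility study. Its planners could read an empty safety record as reassurance that the record cannot give.

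**Working it through.** **Step 1. The plan's own figure.** The only computed design figure is a power of 1.0 for the SHAP comparison (Statistical Design and Power: N = 6, effect size 3, α = 0.05, one-sided alternative, two-sample t-test). It reproduces. With six observations per condition, 10 degrees of freedom and noncentrality 3/√(2/6) = 5.20, power is 0.9992. This concerns efficacy only; the plan gives no safety figure.

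**Step 2. Possible harms against the stated safeguards.**

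| Possible event | Safeguard in the plan | Does it need sensation? |
|---|---|---|
| Malfunction | Staff observation, switch-off, manual removal | No |
| Pinching | Thin glove, mechanical stops | No |
| Motion beyond natural range | Mechanical stops, software shutdown | No |
| Pressure or strain with the device working normally | Individual adjustment for comfort; reported discomfort; general clinical presence | The first two, yes |

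The gap is the last row. Sustained load needs no fault: the Aim 1 Research Design describes actuators that cannot be driven backwards, hold position against opposing force and keep grip force without drawing current.

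**Step 3. Could it be found afterwards?** Open wounds are excluded at entry, but no matching look at the hand after use is stated. Images of the hand are optional and not tied to any time point. The only possible repeat visit (Aim 2, Potential Problems) is conditional and concerns performance.

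**Step 4. What an empty record could mean.** Neither an injury rate nor a detection probability is in the documents, so both are assumed here. Let p be the true rate of device-related injury per participant and d the proportion of injuries that would be detected and recorded.

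- Exact one-sided 95% upper limit for 0 of 6 with d = 1: 1 − 0.05^(1/6) = 0.393. As the upper end of a two-sided 95% interval: 1 − 0.025^(1/6) = 0.459.
- With d < 1 the limit on the true rate is 0.393/d: 0.52 at d = 0.75, 0.79 at d = 0.50, and above 1 (no information) at d = 0.25.
- Probability that none is recorded among six = (1 − p·d)^6:

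| Assumed p | d = 1 | d = 0.75 | d = 0.50 | d = 0.25 |
|---|---|---|---|---|
| 5% | 0.735 | 0.795 | 0.859 | 0.927 |
| 10% | 0.531 | 0.626 | 0.735 | 0.859 |
| 20% | 0.262 | 0.377 | 0.531 | 0.735 |
| 30% | 0.118 | 0.217 | 0.377 | 0.626 |

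Six participants say little about safety even with perfect detection. Incomplete detection removes much of what is left: at p = 20%, halving detection doubles the chance of an empty record, from 0.26 to 0.53.

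**The case against.** The strongest reply is that the study does not rely on the participant alone. Therapists and other medical professionals watch throughout, and what they see does not depend on the participant's sensation. The mechanical and software stops do not depend on it either. The rings may leave the finger pads visible, the glove comes off at the end in a medical facility, and participants are recruited from patients under treatment at that clinic. All of this stands. It rules out several stronger conclusions that a reader might infer:

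- *That monitoring has no working signal for a participant without sensation.* Observation is continuous; malfunction and discomfort are what it looks for, not what starts it.
- *That an injury appearing later would never be seen.* A one-time study does not exclude later contact, and the clinic may see the participant again.
- *That missed injuries would be counted as none.* No adverse-event count is planned, and feasibility is judged on SHAP alone. The risk is an unrecorded event and a silence open to misreading.
- *That the stated force implies a harmful pressure on the skin.* The phrase "sufficient force output to prescribe a fingertip force exceeding 40 N" describes actuator capability, not force used in a session, and no contact area is given.

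Two further limits apply. The sensation wording in Specific Aims belongs to a long-term objective and speaks of varying levels, so the number affected could be zero. And not every page was available for review; one part directly after the Data and Safety Monitoring Plan was missing, so adverse-event provisions could sit there.

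What the reply does not supply is an instruction to look at the hand after use, or a field in which to record the result. Staff may well inspect it unprompted, but the plan neither asks for this nor captures it.

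**Conclusion.** The point holds in a limited form. As written, discomfort is one of only two named things to watch for, and it cannot be relied on in hands that the eligibility criteria admit. For pressure or strain from a normally working device, the text available provides neither an observed check after use nor a record of the result.

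Its size cannot be fixed from the documents. Between none and all six participants may lack sensation. The 39% limit follows from N = 6 alone; the 52% and 79% limits and the table in the working rest on assumed detection proportions and injury rates and are illustrative. The conclusion does not depend on them.

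This should be changed before the first participant is tested, because the remedy is cheap and the data cannot be recovered afterwards. It does not affect the SHAP comparison, and it is not evidence that the device is unsafe.

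**What to change.** 1. Reconcile the monitoring sentence in Adequacy of Protection Against Risks with the descriptions of sensory loss in Specific Aims and the Aim 1 Research Design, so that monitoring does not rest on reported discomfort.
2. Have the therapist who is already present record whether the hand has sensation, and the condition of the hand and wrist before fitting and after the device is removed.
3. Add these findings, and any device-related adverse events, to the data lists in Risks to Human Subjects and the Data and Safety Monitoring Plan.
4. Reconcile the glove under the device (Pinch Points) with the exposed finger pads (Aim 1 Research Design), so that it is clear which skin can be seen during use.
5. In the report, give the number of participants with and without sensation beside any safety statement, with the exact upper limit where no events are recorded.

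Whether later contact is needed, and all action thresholds and timing, are for the clinical lead. The cost is wording in a few sections, a short form, and a few minutes per visit from staff already in the room.
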